**A Prospective Randomized Multicenter Trial Comparing Performance of Two
Intracorporeal Lithotripters for Removal of Large Renal Calculi**

The ShockPulse-SE vs. Trilogy Trial

CLINICAL INVESTIGATION PLAN

Coordinating Principal Investigator	[name] [name] Professor of Urology Indiana University Health Physicians [name] [contact] Email: [contact]
--	--

Protocol Synopsis

A Prospective Randomized Multicenter Trial Comparing Performance of Two Intracorporeal Lithotripters for Removal of Large Renal Calculi - The ShockPulse-SE vs. Trilogy Trial
	
Study Objective(s)	To compare the performance, as measured by the stone clearance rate at time of percutaneous nephrolithotomy, of the ShockPulse-SE Lithotripsy System to the Trilogy Lithotrite.
Study Devices	
 1. ShockPulse-SE Lithotripsy System with the 3.76 mm probe 2. Trilogy Lithotrite with 3.9 mm probe
Indications for Use	
Both devices are cleared for use in the USA for the following indications:
 
 1. The ShockPulse-SE Lithotripsy System is intended to be used for fragmentation of urinary tract calculi in the kidney, ureter, and bladder. 2. The Trilogy Lithotrite is intended to be used to fragment urinary tract calculi in the kidney, ureter, and bladder.
Device Sizes	
 1. Shock Pulse-SE 3.76 mm lithotripsy probe 2. Trilogy 3.9 mm Probe
Study Design	Prospective, randomized, multicenter, 2 arm, comparative trial
Planned Number of Subjects	N=100
Planned Number of Investigational Sites / Countries	A total of 3 sites in the USA
Primary Endpoint	
Stone clearance rate defined as the kidney stone surface area measured by pre-operative computed tomography (CT) scan divided by the time to remove the targeted stone burden.
 
 • Time to remove the targeted stone burden is measured at time the lithotripter unit starts fragmenting the stone to time all fragments are removed from the kidney based on visual inspection. This is prior to final visual inspection of the kidney with a flexible nephroscope.

Additional Endpoints	
Additional endpoints include the following:
 
 1. Device malfunctions 2. All complications measured by the Clavien Classification of Surgical Complications 3. Stone free status as defined by the presence or absence of stone material on postoperative CT imaging and at final follow up 
 • Stone free status must be assessed postoperative day 1 by CT scan.
Method of Assigning Patients to Treatment	
The patients will be block randomized 1:1 to either stone removal with the Trilogy or the ShockPulse –SE device.

Follow-up Schedule	
 1. Baseline (Clinic Visit) – within 3 months prior to surgical procedure 2. Procedure (Hospital Visit) 
 • Stone free status may be assessed at this time by CT scan on Postoperative day 1 3. 6-12 Week Follow-up Visit (Clinic Visit) 
 • Stone free status may be assessed at this time by KUB scan and/or ultrasound, or CT scan 4. End of Study 
 • End of study will be reached after completion of the 6-12 Weeks Follow-up Visit, subject withdrawal or lost to follow-up, whichever occurs first.
Study Duration	
It is anticipated that this study will take 12 months to complete once IRB approval is obtained at all participating locations.

Key Inclusion Criteria	
 1. ≥ 18 years of age 2. Stone burden ≥ 1.5 cm as measured on preoperative CT scan 3. Patient is scheduled to undergo a percutaneous nephrolithotomy procedure 4. Willing and able to provide informed consent
Key Exclusion Criteria	
 1. Pregnant 2. Active urinary tract infection 3. Prior shock wave lithotripsy within 3 months of study procedure 4. Multiple percutaneous access sites are anticipated 5. Unable or unwilling to provide informed consent
Statistical Methods	
Primary Statistical Hypothesis	We hypothesize that the Trilogy will increase the stone clearance rate by 25% compared to the Shockpulse-SE
Statistical Test Method	Outcomes between treatment groups will be assessed using a t-test to compare means. Values of $p \leq 0.05$ will be considered significant.
Sample Size Parameters	For simplicity, sample size calculations were performed using a two-sided Student t-test with a power of 90% and a significance level of alpha = 0.05. The primary outcome of interest is the clearance rate of the targeted stone burden. Preliminary in vitro data shows a reduction of approximately 50% in the average lithotripter clearance time of a 1 cm^3 BegoStone for the Trilogy lithotrite compared to the ShockPulse-SE. Given the increased variability of use in vivo and across subjects, a more conservative difference was considered for sample size estimation. Assuming a 25% improvement in clearance rate that results in an effect size of 0.7, a sample size of 44 subjects in each group is required. To account for the possibility of unevaluable data a total of 100 patients, 50 in each group will be enrolled.

Introduction

Large and complex renal calculi, defined as those with a maximum diameter of ≥ 1.5 cm, can be removed from the upper urinary tract by percutaneous nephrolithotomy but the stones usually require fragmentation in order to remove them through the access site. There are a number of commercially available intracorporeal lithotripters used to fragment or break kidney stones to allow elimination including pneumatic, ultrasonic, and combination devices. Each technology has its own relative advantages and disadvantages.

New versions of intracorporeal lithotripter devices have been introduced with improvements meant to address prior functional limitations such as probe clogging or breaking and cumbersome hand piece design.

The Trilogy lithotrite is the newest generation device stone fragmentation device from Boston Scientific. The Trilogy device uses unique technology to efficiently fragment and remove stone material, superior to other devices on the market based on preliminary bench testing. From Olympus, the ShockPulse-SE Lithotripsy System (Cyberonics, Erie, PA, USA) is a constant ultrasonic wave energy lithotripter with intermittent shock wave (ballistic/mechanical) energy. The ShockPulse-SE has a single probe design with an OD of 3.76 mm which allows for larger sized stone fragments to be vacuumed from the urothelium. The larger, single lumen also allows for a high flow rate to reduce probe clogging events. The end result is faster stone clearance rates based on in vitro studies (company brochure).²

The objective of this study is to compare the performance, as measured by the stone clearance rate at time of percutaneous nephrolithotomy, of the ShockPulse-SE Lithotripsy System to the Trilogy lithotrite when used for large complex renal calculi.

2. Device Description

The Trilogy has been FDA cleared for fragmentation of urinary tract calculi in the kidney, ureter, and bladder. Trilogy is a combined piezoelectric/pneumatic device capable of fragmenting calculi and aspirating stone debris. The novel technology in Trilogy has been demonstrated in bench testing to more quickly disintegrate stones compared to other devices. The following components are included in the Trilogy System:

REF	Description	
Trilogy Parts	Trilogy Lithotrite	
	M0068402010	Swiss LithoClast® Trilogy Console
	M0068402030	Swiss LithoClast® Trilogy Handpiece Kit
	M0068402050	Swiss LithoClast® Trilogy Foot Switch
	M0068403590	Trilogy Reusable Torque Wrench
	M0068401890	Quick Guide
	M0068401810	Stone Catcher Holder
	M0068401800	HDMI-VDI cable (10m)
	M0068401820	Filling Bottle
	M0068401830	Bottle of Demineralized Water (2.5l)
	M0068401850	Power Cord (US - 6m)
	M0068401860	Swiss LithoClast® Trilogy System IFU
	M0068403540	3.9mm x 350mm Trilogy Probe Kit
	M0068403550	3.9mm x 440mm Trilogy Probe Kit
	M0068402980	Stone Catcher for Trilogy

The ShockPulse-SE Lithotripsy System has been FDA cleared fragmentation of urinary tract calculi in the kidney, ureter, and bladder. The ShockPulse-SE System is an electromechanical device capable of fragmenting calculi and aspirating stone debris. The novel technology in the ShockPulse-SE Lithotripsy System uses a single transducer and proprietary ShockPulse technology to generate both low-frequency mechanical impacts and high-frequency ultrasonic energy which quickly disintegrates stones. The following components are included in the ShockPulse System:

REF	Description	
SPL-S	ShockPulse-SE Lithotripsy System	
	SPL-T	ShockPulse Lithotripsy Transducer
	SPL-CSL	ShockPulse Lithotripsy Cleaning Stylet - Large
	SPL-W	ShockPulse Lithotripsy Wrench
	SPL-PC	ShockPulse Lithotripsy Power Cord
	SPL-G	ShockPulse Lithotripsy Generator

	SPL-NC	ShockPulse Lithotripsy Nose Cone
	SPL-IFU	ShockPulse Lithotripsy Instructions for Use
	SPL-PDBX376	ShockPulse Lithotripsy Probe, Sterile Single Use, 3.76 mm (3/Box)

Study Objectives

To compare the performance, as measured by the stone clearance rate at time of percutaneous nephrolithotomy, of the ShockPulse-SE Lithotripsy System to the Trilogy Lithotrite.

Study Endpoints

Primary Endpoint

Stone clearance rate defined as the kidney stone surface area measured by preoperative computed tomography (CT) scan divided by the time to remove the targeted stone burden.

Time to remove the targeted stone burden is measured at time the lithotripter unit starts fragmenting the stone to time all fragments are removed from the kidney based on visual inspection. This is prior to final visual inspection of the kidney with a flexible nephroscope.

Additional Endpoints

1. Device malfunctions
2. All complications measured by the Clavien Classification of Surgical Complications

Stone free status as defined by the presence or absence of stone material on postoperative day 1 CT imaging

This study is a post-market, prospective, randomized, multicenter, 2-arm, comparative trial.

Scale and Duration

A total of 100 subjects will be enrolled and treated at 3 study sites across the USA. Each subject will be followed for approximately 6-12 weeks after the study procedure. It is anticipated for the entire study to last approximately 12 months.

***All sites will perform 10 independent PCNL cases, outside of the study period, using the Trilogy lithotrite to become accustomed with the device prior to enrolling patients.**

Treatment Assignment

The patients will be block randomized 1:1 to either stone removal with the Trilogy or the ShockPulse–SE device. All randomization will occur at the central study site via computer randomization by the statistician to limit selection bias.

Justification for the Study Design

This study will compare performance of two devices for the treatment of large renal calculi. The study has been designed as a prospective, multi-centric, randomized, comparative study. The intent of this design is to minimize bias and to allow for statistical comparison of the two treatment groups.

Subject Selection

Study Population and Eligibility

Patients who meet all of the inclusion criteria and none of the exclusion criteria will be considered for inclusion in the study.

Inclusion Criteria

1. ≥ 18 years of age
2. Stone burden ≥ 1.5 cm as measured on preoperative CT scan
3. Patient is scheduled to undergo a percutaneous nephrolithotomy procedure
4. Willing and able to provide informed consent

Exclusion Criteria

1. Pregnant
2. Active urinary tract infection
3. Prior shock wave lithotripsy within 3 months of study procedure
4. Multiple percutaneous access sites are anticipated
5. Unable or unwilling to provide informed consent

Subject Accountability

Point of Enrollment

A subject will be considered enrolled in the study if they meet all eligibility criteria and after the subject signs and dates the informed consent form (ICF). No study-related procedures can take place until the ICF is signed.

Withdrawal

All subjects enrolled in the clinical study (including those withdrawn from the clinical study or lost to follow-up) shall be accounted for and documented. If a subject withdraws from the clinical investigation, the reason(s) shall be reported. If such withdrawal is due to problems related to study device safety or performance, the investigator shall ask for the subject's permission to follow his/her status/condition outside of the clinical study.

Reasons for withdrawal include:

- Physician discretion
- Subject choice to withdraw consent
- Lost to follow-up
- If the subject dies due to any cause

While study withdrawal is discouraged, subjects may withdraw from the study at any time, with or without reason, and without prejudice to further treatment.

If any treated study patient is unable to return to the study center after treatment, efforts will be made to obtain complete follow-up information from the patient's primary physician. The reason for a patient's failure to return for the necessary follow-up visits or for a patient's discontinuance from the study must be determined and recorded in the case report forms (CRF).

All applicable CRFs up to the point of subject withdrawal must be completed. Subjects who are "lost to follow up" should have documented attempts to contact them.

Additional data may no longer be collected after the point at which a subject has been withdrawn from the study or withdraws his/her consent, for whatever reason. Data collected up to the point of subject withdrawal may be used for study analysis.

Study Methods

Data Collection

The schedule of data collection is illustrated in Table 2.

Procedure/Assessment	Screening/Base line (Clinic Visit)	ShockPulse-SE or Trilogy Procedure (Hospital Visit)	Follow-up Visits	
			6-12 Week Visit ³ (Clinic Visit)	Unscheduled Visit ² (Clinic Visit)
Visit Window	Within 90 Days Prior to Procedure			
Informed Consent Form	X			
Selection Criteria	X			
Randomization	X			
Demographics	X			
CT Scan& Stone Information	X			
Medical History	X			
Pre-operative Physical Exam and Laboratory Data		X		
Lithotripsy Procedure		X		
Stone Free Status		X ¹	X ¹	
Post-operative Stone and Laboratory Data		X		
Device Malfunctions		X		
Adverse Events		X	X	X

¹Stone Free Status must be assessed on POD 1 by CT. ²Unscheduled Visits may be performed between protocol specified visits as deemed appropriate by the investigator.³End of study will be reached after completion of the 6-12 Week Follow-up visit, subject withdrawal, or lost to follow-up, whichever occurs first.

Informed Consent

All subjects taking part in this clinical study must undergo the informed consent process. Subjects must be allowed adequate time to review the consent, raise questions, and make a voluntary decision to participate in the clinical study. Each subject must sign and date the IRB approved informed consent form before any clinical study-related procedures are performed. A copy of signed informed consent form will be provided to the subject for his/her records. A subject's participation in the clinical study begins with the signing and dating of the informed consent form.

Screening (Clinic Visit):

The following data will be captured during the Screening Visit:

- Informed consent process
- Inclusion / exclusion criteria
- Randomization
 - All randomization will occur at the central study site via computer randomization by the statistician to limit selection bias

Baseline (Within 90 Days Prior to Procedure) (Clinic Visit):

The following data will be captured during the Baseline Visit:

- Demographics
- CT scan
- Stone burden
- Stone size (cm)
 - Axial x Coronal
- Targeted stone surface area (mm²)
 - This measurement is determined by outlining the CT image of the stone using a digital system such as PACS)
- Previous treatment of targeted stone
- Medical history
- Pre-operative physician exam
 - Height, weight, and BMI
- Pre-operative laboratory data
 - Serum creatinine (mg/dl)
 - Hemoglobin (g/dl)
 - Hematocrit (%)
 - Na (mEq/l)
 - Urine culture

ShockPulse-SE or Trilogy Procedure (Hospital Visit):

The following data will be captured during the Lithotripsy Procedure Visit:

Intraoperative Data:

- Date of surgery
- Device accountability
 - The lot number of the disposable devices used shall be captured.
- Type of Anesthesia
 - General
 - IV Sedation
 - Regional
- ASA Level
 - 1: A normal, healthy patient
 - 2: A patient with mild systemic disease
 - 3: A patient with severe systemic disease
 - 4: A patient with severe systemic disease that is a constant threat to life
- Number and location of access sites for lithotripsy procedure
- Total procedure time as measured in minutes from induction of anesthesia to end of anesthesia
 - **Please ensure these time points exists in the subject's source documentation**
- Time to clearance of targeted stone burden as measured in minutes
 - Start time: When the investigator begins to use the lithotriptor on the targeted stone
 - Stop time: When the investigator has cleared all fragments and prior to final inspection of the kidney with the flexible nephroscope
 - **Please ensure these time points exists in the subject's source documentation**
- Use of other intracorporeal lithotripsy devices including laser
- Settings utilized for each lithotripter device
- Stone Free Status
 - Assessed by CT scan performed postoperative day 1.
- Estimated blood loss (EBL)
- Device malfunctions
- Adverse events

2.1.1.Post-operative Data:

- Length of hospitalization measured in days
- Need for blood transfusion
- Assessment of nephrostomy tube
- Adverse events
- Stone Free Status
 - Date of imaging study should be provided.
- Stone analysis
- Stone culture results
- Post-operative laboratory data
 - Serum creatinine (mg/dl)
 - Hemoglobin (g/dl)
 - Hematocrit (%)

- Na (mEq/l)

6-12 Week Follow-up Visit (Clinic Visit):

The following data will be captured during the 6-12 Week Follow-up Visit:

- Stone Free Status
 - Date of imaging study should be provided. Either a CT or KUB and/or Ultrasound is required prior to or during the 6-12 Week Follow-up Visit.
- Adverse events

Unscheduled Visit (Clinic Visit):

Unscheduled visits may be performed between visits required by the protocol as deemed necessary by the investigator. Data for unscheduled visits will be captured on the Adverse Event case report form (CRF).

End of Study

End of study will be reached after completion of the 6-12 Week Follow-up visit, subject withdrawal, or lost to follow-up, whichever occurs first.

Source Documents

Source documents are the patient records maintained at the study site. In most cases, the source documents will be the physician's or hospital's patient chart. In some cases, the source documents may be electronic. In both cases, the information captured in the CRF must match the information in the chart or electronic source document.

Statistical Considerations

Endpoints

Primary Endpoint

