The primary outcome, clearance rate, will be calculated by dividing the stone surface area by the clearance time. To compare the clearance rate between groups a mixed effects model will be used including treatment group as a fixed effect and site (hospital) as a random effect. Any demographics that were found to be unbalanced between groups may also be included in the model as covariates.

Device malfunctions will be recorded and summarized by treatment group. The proportion of cases experiencing device malfunctions will be compared between groups using Fisher's Exact test. All subject complications will be recorded and summarized using the Clavien Classification of Surgical Complications. The proportions of subjects experiencing complications will also be compared between groups using Fisher's Exact test. The number (and percent) of patients found to be stone free at 6-12 weeks post-op will be summarized and compared between groups using Fisher's Exact test.

The main analysis of the primary endpoint will be performed on the ITT dataset. Supportive analyses may be performed on the PP dataset. All reporting and analysis of adverse events and complications will be done using the SA data set.

Control of Systematic Error/Bias

To minimize selection bias there will be a single randomization schedule managed at the lead investigative site. Upon subject enrollment, all participating sites will contact the main site for experimental group randomization. The randomization will be a permuted block randomization that will help ensure a reasonable balance of group assignment throughout the study enrollment period.

Number of Subjects per Investigative Site

The maximum number of subjects for any single site is 85.

Data Management

Data Collection, Processing, and Review

Subject data will be recorded in a limited access, secure, web-based electronic data capture (EDC) system called REDCap. REDCap is designed to comply with HIPAA regulations. REDCap is not 21 CFR Part 11 compliant; however, this data will not be submitted to the FDA as it is part of a post-market study comparing two commercialized devices for their cleared intended uses.

The conduct of clinical studies pertaining to the use of electronic records and signatures. Database backups are performed regularly.

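### Withdrawal for any reason, including by the physician without loss of consent, ends data collection, so later complications of treated subjects go unrecorded although all 30-day events are to be graded

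*Combined protocol and SAP*

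**What the plan says.** Four parts of the combined protocol and SAP bear on this.

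- **Subject Accountability, Withdrawal.** The stop rule reads "Additional data may no longer be collected after the point at which a subject has been withdrawn from the study or withdraws his/her consent", and the sentence goes on to apply it whatever the reason. The listed reasons include "Physician discretion", with no limit to the period before treatment. For one group there is a further rule: "If such withdrawal is due to problems related to study device safety or performance", then "the investigator shall ask for the subject's permission to follow his/her status/condition outside of the clinical study". Earlier data are kept: "Data collected up to the point of subject withdrawal may be used for study analysis".
- **End of Study.** Withdrawal closes the study for that subject: "End of study will be reached after completion of the 6-12 Week Follow-up visit, subject withdrawal, or lost to follow-up, whichever occurs first". The Synopsis follow-up schedule and the third footnote to the data collection table say the same.
- **Statistical Considerations.** The Safety Analysis (SA) set holds every subject who received any treatment on protocol. "All reporting and analysis of adverse events and complications will be done using the SA data set". The planned comparison is the proportion of subjects with complications, by Fisher's exact test.
- **Clavien Classification of Surgical Complications.** Every adverse event during surgery or in the 30 days after it is to be graded.

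**The concern.** The stop rule joins two different events with an "or"-type construction: being withdrawn, and withdrawing consent. Only the second obliges the study to stop collecting data. A subject withdrawn by the physician may be quite willing to be followed. A subject who leaves over a device problem and agrees to further follow-up has given the permission needed, yet the protocol places that follow-up outside the study.

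Such a subject, once treated, remains in the SA denominator while any later complication has no route into the numerator. Safety is an additional endpoint on which two devices are compared. The operator necessarily knows which device was used, and withdrawal can be related to how it performed, so the loss could differ between arms. The combined safety summaries for the DSMC at 50 and 100 subjects would carry the same gap if they are built from the study data.

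**Working it through.** **1. The passages side by side, for a treated subject withdrawn before day 30 without withdrawing consent.**

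| Question | Where | Answer |
|---|---|---|
| Is the subject in the SA set? | Analysis Sets | Yes, any treatment suffices |
| Do events before withdrawal count? | Withdrawal | Yes |
| Are events after withdrawal collected? | Withdrawal; End of Study | No |
| Are all events to day 30 to be graded? | Clavien Classification | Yes |

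The last two rows cannot both be met. The investigator's general duty to record every adverse event does not settle the matter, because it applies only as the protocol provides. No passage returns outside follow-up to the case report form or the SA analysis, and no sensitivity analysis covers withdrawn subjects.

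**2. When the planned comparison changes.** I assume that a subject with no recorded complication counts as having none; the plan does not say how withdrawn subjects are scored.

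- Complication recorded before withdrawal: the subject is already in the numerator, so the proportion does not change. Later events, and possibly a higher Clavien grade, are lost.
- First complication after withdrawal: the subject is counted as uncomplicated, so the proportion is too low.

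The exposed period runs from withdrawal to day 30 for Clavien grading, and to the 6-12 week visit for adverse events generally.

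**3. Arm size.** The Sample Size section gives effect size 0.7, two-sided alpha 0.05 and power 90%. The two-sample t-test needs 43.87, so 44 per group, as stated. Enrolment is 50 per group, leaving 50 − 44 = 6 for unevaluable data. These figures belong to the primary endpoint; here they only supply n = 50.

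**4. Size per subject.** With m subjects in an arm whose first complication follows withdrawal, the understatement is 100 × m / 50 percentage points:

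- m = 1: 2 points
- m = 3: 6 points
- m = 6 (the whole allowance, as an upper yardstick and not a forecast): 12 points

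The error in the difference between arms is 100 × (m₁ − m₂) / 50, so equal losses cancel in the difference.

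**5. Effect on the test.** All counts below are assumed. Two-sided Fisher's exact test, 50 per arm, with cases hidden in the worse arm:

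| Assumed true counts | None hidden | One hidden | Two hidden |
|---|---|---|---|
| 2 v 10 | 0.028 | 0.051 | 0.092 |
| 4 v 13 | 0.031 | 0.054 | 0.091 |
| 5 v 15 | 0.023 | 0.040 | 0.066 |
| 2 v 12 | 0.008 | 0.015 | 0.028 |
| 4 v 10 | 0.148 | 0.234 | 0.357 |

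One or two hidden cases matter when the true result lies near 0.05, and do not alter the conclusion when it lies well to either side.

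**The case against.** The strongest reply is that the sentence on outside follow-up protects patients. Read in order, it concerns a subject who chooses to leave, and it offers continued follow-up to someone who would otherwise have none. Stopping collection when consent is withdrawn is proper. Nothing says that a device failure prompts the physician to withdraw a patient: malfunctions and the use of other lithotripters are recorded as study data, and the ITT set keeps subjects whatever treatment they received. Treatment is a single procedure, so intra-operative events and in-hospital events before withdrawal are captured. The comparison is secondary, and the sample size was not set for it.

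Most of this stands, and it rules out several stronger readings that a reader might infer.

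- *That patients with device problems drop out of the safety comparison.* They do not. Treated subjects stay in the SA set and their events up to withdrawal count.
- *That the subjects lost are those most likely to have been harmed.* This is plausible, but the documents give no data for it.
- *That the results are biased towards the device that fails more often.* A differential loss is possible, but the documents do not establish it. For stone-free status at 6-12 weeks even the direction is open, because the plan does not say whether a missing result is excluded or counted as not stone free. The day 1 CT is affected only by withdrawal before that scan.
- *That physician-withdrawn subjects are expressly sent to outside follow-up.* The wording speaks of a subject who withdraws; whether it extends to physician withdrawal is unclear.

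The reply does not answer the stop rule itself. That rule covers physician withdrawal as well as withdrawn consent, and it keeps out follow-up that the subject has agreed to.

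**Conclusion.** The point holds as a conflict of rules with a limited safety consequence. Followed as written, the Withdrawal and End of Study text prevents collection of complications after withdrawal in treated subjects who may still consent to it, contrary to the commitment to grade all events to day 30. The any-complication proportion is understated by about 2 percentage points for each subject in an arm of 50 whose first complication follows withdrawal, assuming that no recorded event is scored as no event. The overall size and any imbalance between arms are unknown, since neither withdrawal nor complication rates are stated; the p-values show sensitivity and not an expected effect. The primary endpoint is measured during the procedure and is essentially unaffected. The change should be made because it is cheap and the rule is explicit, but it does not threaten the trial's main conclusion.

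**What to change.** 1. In the Withdrawal section, separate withdrawal by the physician from the subject's withdrawal of consent to data collection, and let only the latter end collection.
2. For treated subjects who have not withdrawn that consent, or who permit continued follow-up after a device-related withdrawal, record adverse events through the scheduled follow-up in the case report form and include them in the SA analysis. Record any imaging that is obtained. A refusal of further data collection is respected in every case.
3. Amend the End of Study wording in the Synopsis, the table footnote and the End of Study section to match, and reconcile all three with the 30-day Clavien statement.
4. Reconcile the listing of loss to follow-up as a withdrawal reason, which stops collection, with the instruction to seek information from the primary physician for treated patients who cannot return.
5. Report withdrawals by arm, reason and timing relative to treatment.

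The cost is protocol and consent-form wording and a few extra follow-up contacts for subjects who would otherwise have been closed out.
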